**N°ID-RCB: 2020PI095**

**Update 10 / 08 / 2021**

Acronym : PRODDIGE  Full title: Digital solution to improve cognitive function in epilepsy: PRODDIGE project

1.1 Research characteristics

 
- Clinical research
 
- Multicentric
 
- Transversal : patient / normal control
 
- Randomized trial
 

1.2 Product(s)/strategy observed in the research

Randomized controlled trial to evaluate the use of a digital solution on epileptic patients' cognitive complaint about lexical access disorder.

1.3 Research Rationale and Working Hypotheses

Epilepsy is one of the most common chronic neurological conditions. It leads to cognitive disorders in 20-50% of patients. In comparison to seizures, these cognitive disorders are a major additional factor in occupational, social and family disability. They are particularly frequent (50%) in temporal epilepsies and concern most of time memory and language skills. These disorders are well described, multifactorial, but no therapy (drug and/or non-drug) has yet been validated (Brissart & Maillard 2018).
 
Recently, cognitive rehabilitation techniques have shown benefits in some neurological pathologies, such as multiple sclerosis (Brissart et al. 2020).
 
In adult epilepsy, few cognitive remediation studies that have been conducted have significant methodological shortcomings that limit the scope of their results (for review Del Felice et al, 2017; Joplin et al, 2018).
 
Studies have shown promising results in attention and memory (Engelberts et al., 2002; Helmstaedter et al., 2008) but in language, no study has been published.
 
Our objective is to evaluate the effectiveness of a digital solution with language exercises in epileptic patients.

1.4 Main Objective

Evaluate the use of digital solution in total autonomy and compare it to the use of a neuropsychologist-supervised via teleconsultations with a sample of epileptic patients.

1.5 Primary endpoint

Number of weekly connections of epileptic patients in each group.

1.6 Secondary objectives

To compare the cognitive and behavioral abilities of patients before and after the program:
 
 
- Feeling the frequency of lexical access problems
 
- Self-esteem,
 
- Score and speed of oral naming
 

- Verbal fluency
- Information processing speed
- Selective and sustained attention
- Short-term memory
- Working memory
- Mental flexibility capabilities
- Mood
- Anxiety

### **1.7 Secondary Evaluation Criteria**

Scores at :

- Questionnaire language score (0 to 12 points)
- Depression scale score (Neurological Disorder Depression Inventory for Epilepsy : NDDI-E) : 6 to 24 points : 6 better outcome
- Anxiety scale score (Generalized Anxiety Disorder: GAD-7): 0 to 21 points : 0 better outcome
- Self-esteem score (Rosenberg scale): 0 to 40 points: 40 better outcome
- Number of correctly named words and response time (Batterie d'Evaluation des Troubles Lexicaux) : 0 to 50 points : 54 = better outcome
- Computerized Speed Cognitive Test (CSCT): processing speed index: number of correct items in 90 sec. 0 to 110 points : 110 = better outcome
- Immediate memory: digit span: number of digits recalled correctly in location order: 0 to 9 score : 9 = better outcome
- Working memory: backward digit span: number of digits recalled correctly in inverse order: 0 to 9 score : 9 better outcome
- Selective Attention Test: Paced Auditory Serial Audition Test 4 seconds (PASAT): 0 to 60 score : 60 = better outcome
- Verbal Initiation Test: Phonological Fluency: number of words beginning with P given in 2 minutes: 0 to 50 words : 50 = better outcome
- Category fluency test: number of words given in 2 minutes that belong to the category of Animals: 0 to 50 words : 50 = better outcome
- Boston Naming Test (BNT): number of correctly named words (0 to 50 points) and response time in seconds : 50 = better outcome
- Lexicon access tests (Denomination Orale 80): number of correctly named words (0 to 80 words) and response time in seconds : 80 = better outcome

### **1.8 Number of Subjects required**

Main hypothesis: Investigators postulate that the group of participants supervised by a psychologist via teleconsultations will have an average weekly number of connections at least twice as high as that measured in the total autonomy group.

Secondary hypothesis: Participants who use the solution should have a lower frequency of lexicon access disorders than participants who do not use it. This study should make it possible to assess its extent and discuss its clinical relevance.

To test these hypotheses, 3 groups of participants will be constituted:

- 1 group "application supervised by a psychologist via teleconsultations" (n=30)

- 1 group "application in total autonomy" (n=30)  
- 1 "control" group without using the application (n=30).  
A 4th group of "healthy controls" (n=70) will also be needed to calculate the "reliable change index" (an index that evaluates the potential learning effect when a cognitive test is performed twice over a period of less than one year). The larger size of the latter group is justified by the expected higher number of people lost to follow-up on the second visit.

### 1.9 Description / Subject Recruitment Methods

Healthy controls will be matched to participants on age (+/-5 years) and socio-educational level (+/-2 years of study).

All subjects will be seen during a consultation.

Participants will be recruited through their neurologist or neuropsychologist during a consultation as part of their usual follow-up.

Healthy controls will be recruited through posters in the neurology department University Hospitals, and in the practices of private neurologists

### 1.10 Are there any specially protected persons involved in your research?

NON  OUI

### 1.11 Criteria for inclusion of subjects

#### Inclusion criteria of epileptic participants:

Patient with epilepsy, according to Fisher et al. (2005) criteria: all type of epilepsy could be include (new-onset and drug-resistant)

Treatment must have been stable for 4 months: have the same molecule

Person who has received full information about the organization of the research and has not objected to his or her participation and the use of his or her data

Person aged 18 and over

Mandatory affiliation to a social security scheme

Validated cognitive inclusion criterion: having a YES response on the cognitive complaint questionnaire :

A.Spontaneous complaint :

Does the patient spontaneously complain of language difficulties?

B.Subjective complaint :

1. Do you search for your words?

2. Do you sometimes feel like you have the word on the tip of your tongue?

3. Do you sometimes have trouble finding the names of people you know well?

4. Do you ever say one word for another?

#### Inclusion criteria of normal control:

- Individuals who have received full information about the organization of the research and have not objected to their participation and use of their data.

- Person aged 18 and over

- Person with no neurological and/or psychiatric history

### 1.12 Non-inclusion criteria

**Participants :**

Person with another neurological condition

**Participants and normal control :**

A person over the age of majority who is subject to a legal protection measure or who is unable to express their consent.

Person deprived of liberty by a judicial or administrative decision

A person who regularly uses psychoactive substances (cannabis, alcohol, etc.).

**1.13 Methods of information and non-opposition of subjects**

Participants and healthy controls will be informed about the research specifically and individually on the day of the inclusion visit using the information document provided.

Non-opposition of the patient and healthy control will be sought by the investigator prior to any data collection in this research.

**1.14 Search process**

**I. PATIENT COURSE :**

Inclusion visit as part of the usual follow-up:

- Participants and subjects will be informed of the study by an investigator during a consultation at their respective centers.

- A neuropsychologist will carry out the consultations

- After verification of the eligibility criteria by the investigator and presentation of the objectives of the study, an information document will then be given to the patient for an attentive reading.

- After a reflection period, if the patient agrees to participate in the research and has not objected to the use of these data in this research, then randomization will be carried out via an online module (CleanWeb). This individual randomization will be done according to a 1:1 ratio with stratification by age (+/-5 years) and socio-educational level (+/- 2 years of study) and a randomization block of 4.

- The neuropsychological assessment (V1) will be carried out by the psychologist: it consists of questionnaires and cognitive exercises lasting one and a half hours (the cognitive functions tested are listed in paragraph 1.8).

- The characteristics of each patient's epilepsy will be collected from his or her computerized medical record.

Depending on the group obtained by randomization (A/ B / C), the psychologist will present the application to the patient or not, and will inform him or her whether or not he or she will have telephone appointments.

At the end of visit 1, participants will be invited to use the digital application at their convenience for the autonomous group (B). Participants in the teleconsultation group (A) will be called once a week for 16 weeks to follow up on their connection to the application and to check that they do not present any particular difficulties in using it. A link will be provided to download the application. It will be sent to the patient on paper at the end of the visit.

The duration of use of the digital application will be 4 months.

Group C participants do not use the digital application.

➤ **Follow-up visit (V2) = 5 months post-inclusion (research specific)**

During this visit, participants in group A, B or C will undergo a neuropsychological assessment. The patient in group A or B will provide to the psychologist his or her number of connections to the application.

The patient in group A or B will also answer an interview on how he or she feels about using the application.

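### Randomisation is listed before V1 testing and nothing keeps the arm from the testing psychologist, so the baseline of the examiner-administered secondary tests is not protected from knowledge of the arm

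*Protocol*

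**What the plan says.** Section 1.14 (patient course) sets out the inclusion visit as a list. After eligibility has been checked, the information document read and a reflection period allowed, a patient who agrees is randomised: "then randomization will be carried out via an online module (CleanWeb"). The next item reads "The neuropsychological assessment (V1) will be carried out by the psychologist", and V1 is described as "questionnaires and cognitive exercises lasting one and a half hours". Collection of the epilepsy characteristics follows. Then, according to arm, "the psychologist will present the application to the patient or not", and the same psychologist "will inform him or her whether or not he or she will have telephone appointments".

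At V2, the section names the neuropsychological assessment first. It then says that a patient in group A or B "will provide to the psychologist his or her number of connections to the application" and "will also answer an interview on how he or she feels about using the application". Section 1.16 places the download of the connection file at the end of that visit.

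Section 1.15 makes the arm letter (A, B or C) part of the subject code. Section 1.19 analyses the secondary scores by paired before-after tests. The primary endpoint in section 1.5 is the number of weekly connections.

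**The concern.** V1 supplies the before value of every secondary score. Followed in its listed order, section 1.14 generates the allocation before V1 and gives V1 testing to the role that must act on that allocation. An examiner who knows the arm can, without intending to, prompt, time or score differently. Tests that depend on an examiner's handling are the ones at risk: naming, verbal fluency, digit spans and PASAT.

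An arm-related shift in the baseline would look like a change over time in that arm. The reliable change index could not remove it. The index comes from healthy controls, who are not randomised, and it addresses learning on repeat testing.

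**Working it through.** The Protocol gives no figure to reproduce on this point, so the check is a comparison of the text, one line of algebra and one of time.

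**1. Order of steps.** In section 1.14 the sequence is agreement, randomisation, V1 assessment, epilepsy data, then presenting the application or not and telling the patient about calls. The randomisation item is worded sequentially: after reflection and agreement, then randomise. The order still has to be read from the list. The text allows the arm to be known during V1 but does not state that it is.

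**2. Who knows the arm.** V1 is given to the psychologist, and so is acting on the arm. The Protocol does not say who operates CleanWeb or when the psychologist sees the result. I looked for any masking of the psychologist, a separate assessor, or a rule delaying release of the allocation, and found none. The arm letter in the subject code (section 1.15) is a second route by which the arm could be visible during V1, if the full code is written on the V1 forms.

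**3. What the patient knows.** Presenting the application and announcing the calls are both listed after V1. Patient knowledge of the arm at V1 is therefore not shown, and neither is influence on the self-report questionnaires.

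**4. How a shift carries through.** For one arm, let *T* be the true mean change, *s* an arm-related shift in the V1 mean and *u* one in the V2 mean. Then

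observed mean change = (V2 + *u*) − (V1 + *s*) = *T* + *u* − *s*.

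- If *u* = 0, the change is off by −*s*: one for one, with opposite sign.
- If *u* and *s* have the same sign, they partly or wholly cancel.
- If they have opposite signs, they add.

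The Protocol gives no value for *s* or *u*, no standard deviation and no test-retest correlation.

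**5. Which outcomes.** Section 1.16 counts five computerised and three paper-and-pencil tests without naming which are which, so the line between more and less exposed tests cannot be drawn exactly. Weekly connections have no V1 value and are not touched.

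**6. Whether the order can change.** The stratification factors are age and socio-educational level. Neither needs V1 results, so randomisation can wait for V1. Section 1.21 budgets 2.5 hours of neuropsychologist time per patient for V1, and section 1.14 gives 1.5 hours for the assessment: 2.5 − 1.5 = 1.0 hour remains for other tasks, including presenting the application afterwards.

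**The case against.** **The list may not be strictly chronological.** One of its items is a staffing statement, not a step. That is fair, and it is why the point is about what the text leaves open. But the randomisation item is worded as a sequence, and no passage protects V1 under either reading.

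**The trial is necessarily open.** Groups A and B must learn their arm once V1 is over. Nothing requires the examiner to know it during V1, so this part of the exposure is avoidable.

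**The V2 assessor may know the arm anyway.** This stands. Group A's calls are budgeted as neuropsychologist time, and the usage interview takes place at V2. Re-ordering V1 removes *s* but not *u*.

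Three stronger readings are tempting, and the documents do not support them.

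- *The secondary hypothesis itself is compromised.* Section 1.8 states it as "Participants who use the solution should have a lower frequency of lexicon access disorders than participants who do not use it". Sections 1.6 and 1.16 treat frequency as something the patient feels and reports. Its most natural measure is thus a questionnaire, for which no influence at V1 is shown.
- *The type I error is inflated by a definite amount.* Any such figure needs an assumed shift and correlation that the Protocol does not supply. A figure for users against non-users would also describe a test that section 1.19 does not name for the secondary scores.
- *V2 testing is contaminated by the connection count and interview.* Section 1.14 lists the assessment before both, and section 1.16 puts the connection file at the end of the visit. If list order counts as evidence at V1, it must count at V2 as well.

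**Conclusion.** The point holds for V1 and for the examiner-administered secondary tests. As written, section 1.14 places randomisation before the baseline assessment, gives testing and acting on the arm to the same role, and contains no step that withholds the arm until testing is done. This is a risk of bias that the plan leaves open; it is not evidence that baseline scores will be biased.

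Size and direction are unknown, and no error rate should be attached. The conclusion rests on reading the list in section 1.14 as the order of events and on the absence of any masking statement elsewhere in the Protocol. The computerised tests are probably less exposed, and the primary comparison of weekly connections is unaffected. The change is worth making because it is cheap and the exposure is avoidable.

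**What to change.** In section 1.14, state that the V1 questionnaires and tests are completed and recorded first, that CleanWeb randomisation is opened only then, and that the application is presented or not after that. Keep the arm letter of the section 1.15 subject code off the V1 forms.

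For V2, a single confirming sentence is enough: the listed order is followed, with the assessment first, then the connection count and usage interview.

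The cost is a re-ordering within the same visit, with no added visit or staff. The 1.0 hour of budgeted V1 time beyond the assessment is available for presenting the application afterwards. The downsides are that the arm becomes known about 1.5 hours later in the inclusion visit, and that the V2 assessor may still know it.

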**1.15 Modality of de-identification of subjects**

Check the appropriate box(es) :

by a serial number assigned to the inclusion

other identification mode, specify: a number for the number of the center  
- the order number assigned to the inclusion - A letter for the identification Patient (C) versus Witness (T) - subject initials (first letter of the surname and first name) + a letter for randomization (A: application group + teleconsultation), (B: autonomous application group), (C: control group)

The correspondence table that links the patient's identity to his or her inclusion number will be kept in the investigator binder stored with the CRFs in the locked cabinet in box 5 of the Neurology Department.

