## 1.19 Statistical Analysis

Descriptive analysis: The parameters collected will be described in each group by percentages (categorical variables), mean +/- standard deviation, quartiles, and extreme values (continuous variables).

Main analysis: the comparison of the mean number of connections will first be carried out by a parametric (Student's t) mean comparison test or its non-parametric (Man-Withney) equivalent if the hypotheses of normality and equality of variances are not verified. In the case of significant

differences in one or more parameters between the 2 groups compared, these adjustment variables will be introduced into a linear regression model. A stepwise selection method is provided.

Secondary analysis: Before-after comparisons will be performed by tests on paired series, the Student's t-test when the variable to be compared is quantitative (or the Wilcoxon test), and Mac Nemar's Chi2 when the variable to be compared is qualitative.

The value of the "Reliable Change Index" will be obtained in the group of healthy controls by the product of the standard error of the score concerned and the standard deviation of the difference observed at 2 measurement times.

The significance threshold is set at 5%. An a posteriori power calculation is also planned.

The analyses will be performed by the UMDS, using SAS v9.4 software (SAS Institute Inc., Cary, NC, USA).

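### Randomisation is set at 1:1 in blocks of 4, but patients are randomised to three groups of 30; a block of 4 cannot be balanced over three arms

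*Protocol*

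**What the plan says.** Section 1.14 (patient course, inclusion visit) describes individual randomisation through an online CleanWeb module at a "1:1 ratio with stratification by age (+/-5 years) and socio-educational level (+/- 2 years of study) and a randomization block of 4". A few lines later it says what follows for the patient: "Depending on the group obtained by randomization (A/ B / C"), so C is an outcome of that randomisation.

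Three other places bear on the number of arms:

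- Section 1.8: "To test these hypotheses, 3 groups of participants will be constituted". Each has 30 patients, including the control "group without using the application (n=30").
- Section 1.15: the subject code carries "a letter for randomization (A: application group + teleconsultation), (B: autonomous application group), (C: control group").
- Section 1.19: the main analysis is a two-group comparison and refers to "differences in one or more parameters between the 2 groups compared".

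The fourth group, 70 healthy controls, consists of volunteers recruited by poster. They follow a separate course in section 1.14 with no randomisation.

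**The concern.** The ratio and block size belong to a two-arm trial, while the design has three randomised arms. Two people programming a list from this sentence could produce different lists, because it does not say which arm takes the fourth place in each block.

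The more serious possibility is that the module was set up literally, for two groups. Group C would then be outside the randomisation, and the secondary hypothesis in section 1.8, "Participants who use the solution should have a lower frequency of lexicon access disorders than participants who do not use it", would lose its randomised comparator. Sections 1.14 and 1.15 both speak against that set-up, and the protocol does not show what was done.

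A lesser point of wording is that the windows of 5 years of age and 2 years of study given for stratification are the same as the matching tolerances for healthy controls in section 1.9. A tolerance around a person defines a match; it does not define non-overlapping strata.

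**Working it through.** **Inputs.** Ratio 1:1 and block size 4 (section 1.14); three randomised arms (sections 1.8, 1.14, 1.15); 30 per arm, so 3 × 30 = 90 patients (section 1.8). The number of strata is not given and is assumed below.

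**Can the stated rule give 30/30/30?** A block of size b is balanced over k equal arms only if b is a multiple of k.

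- Block of 4, three arms: 4 = 3 × 1 + 1. No balanced split exists; the most even is 2/1/1. Also 90/4 = 22.5, so 90 patients make 22 full blocks plus 2 patients.
- Fixed 2:1:1 within each block: 90 × 2/4 = 45 and 90 × 1/4 = 22.5 twice, against 30 each in section 1.8.
- Literal 1:1 over all 90: 45/45, with no third arm.
- A and B only: 60/4 = 15 full blocks of 2/2. The arithmetic works, but C is not randomised, against sections 1.14 and 1.15.
- Healthy controls as a fourth arm: excluded, since they are not randomised and number 70.
- Block of 3: 90/3 = 30 blocks of 1/1/1. Block of 6: 90/6 = 15 blocks of 2/2/2. Both give 30/30/30 when unstratified.

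**How much would it matter?** I considered only fills of the fourth slot that keep 30 per arm in expectation: an arm drawn at random, or A, B, C in rotation. For each scheme, 20,000 trials of 90 patients were simulated. In stratified runs patients fall at random into equal strata, and the rotation starts at a random arm in each stratum. The gap is the largest arm minus the smallest. The A versus B standard error relative to 30 versus 30 is

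√[(1/nA + 1/nB) / (2/30)].

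For example, 27 versus 30 gives √[(0.03704 + 0.03333)/0.06667] = √1.0556 = 1.027, or +2.7%.

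| Scheme | Strata (assumed) | Gap: median (90th percentile) | A–B standard error, 90th percentile | Gap of 5 or more |
|---|---|---|---|---|
| Block 4, random fourth slot | none | 5 (8) | +2.7% | 51% |
| Block 4, rotating fourth slot | none | 2 (2) | +0.9% | 0% |
| Blocks of 3 | none | 0 (0) | 0% | 0% |
| Blocks of 3 and 6 mixed | none | 0 (2) | +0.1% | 0% |
| Block 4, random fourth slot | 4 | 5 (8) | +2.7% | 54% |
| Block 4, rotating fourth slot | 4 | 2 (4) | +1.0% | 3.7% |
| Blocks of 3 and 6 mixed | 4 | 2 (3) | +0.9% | 1.4% |

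With 8 assumed strata the gaps are 5 (9) for the random fill, 3 (5) for rotation and 2 (5) for the 3/6 mix, with 90th-percentile standard errors of +3.0%, +1.8% and +1.7%.

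**The case against.** The strongest reply is that this is a slip of wording with little consequence. The natural reading is three equal arms with a wrong block size, since sections 1.14 and 1.15 both name C as a randomised group. Allocation would still be random and unbiased. With a rotating fourth slot and 4 strata the precision cost is practically the same as with valid blocks (+1.0% against +0.9%). Stratification leaves incomplete blocks under any scheme, so exact balance is not guaranteed after the correction either. With 20 assumed strata, a gap of 5 or more occurs in 45% of trials with the 3/6 mix, 58% with rotation and 63% with the random fill. Finally, the secondary analysis in section 1.19 consists of paired before–after tests and names no between-group test involving C.

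Most of this stands as a limit on weight. The loss of precision is small. The advantage in balance depends on having few strata, which makes the undefined strata about as important for achieved balance as the block size. The scenario in which C is not randomised is conditional and runs against the protocol's own text.

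It does not remove the contradiction. The ratio and block size are stated outright, so this is not a detail left to the SAP, and no reading of the sentence delivers three equal arms. The hypothesis comparing users with non-users is also stated in section 1.8, whatever tests section 1.19 lists.

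**Conclusion.** The concern holds. The randomisation rule in section 1.14 contradicts the three-arm design in sections 1.8, 1.14 and 1.15 and cannot be programmed as written. This part is integer arithmetic and rests on no assumption.

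The demonstrated harm is modest: no bias, and about 0 to 3% on the A versus B standard error at the 90th percentile. That size assumes 90 patients, a fill that keeps 30 per arm in expectation, and between one and eight equal strata. The reasons to act are that the rule is not reproducible and that the protocol cannot confirm which list the module holds, including whether C is in it. The sponsor should correct it, though it does not threaten the primary comparison.

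**What to change.** Replace the sentence in section 1.14 with: individual randomisation 1:1:1 to groups A, B and C, in permuted blocks whose sizes are multiples of 3 (for example 3 and 6 in random order, not disclosed to centres), stratified by a few non-overlapping age and education classes with cut points set in the randomisation specification. Keep the plus-or-minus windows for matching healthy controls in section 1.9 only. A fixed block of 6 would also resolve the contradiction; mixed sizes are preferred because the trial is open.

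If enrolment has begun, first check what CleanWeb was set to, including that C is in the list. If it already holds a valid three-arm list, correct the text only. If not, change the remaining allocations, record the date and the earlier rule, and adjust for period in the analysis if the allocation ratio changed.

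The cost is one sentence and a check of a module whose design is already budgeted in section 1.21. The downsides are coarser strata and some predictability. For an observer who knows the block rule and every earlier allocation in the stratum, with 11 to 90 patients per stratum:

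- Allocations certain in advance: 6 to 9% with the 3/6 mix, 9 to 12% with blocks of 4 and a random fourth slot, 27 to 33% with fixed blocks of 3.
- Best guess correct: 54 to 58% with the 3/6 mix, 49 to 50% with blocks of 4 and a random fourth slot.

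These are upper bounds; undisclosed sizes and several centres make the real figures lower.

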**I. NORMAL CONTROL COURSE :**

➤ **Inclusion visit (research specific)**

Normal controls are recruited through posters and on a voluntary basis in the 4 centers. They are therefore in contact (telephone or e-mail) with the neuropsychologist of the study on their own initiative. The objectives of the study are then presented during this contact. If the subject gives his agreement, an appointment is fixed in order to carry out the inclusion visit. On the day of the visit, the subject is given an information document that he or she should take the time to read. After a period of reflection, if he agrees to participate in this research and if he does not object to the use of his data within the framework of this research, the acts specific to the research may be carried out (neuropsychological assessment including only cognitive data + collection of clinical characteristics).

➤ **Follow up visit : 5 months post inclusion (research specific)**

During this visit, the normal control will undergo the same neuropsychological assessment as in visit V1 with the neuropsychologist.

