#### **Healthy subjects neuropsychologist time:**

- Estimated neuropsychological time (V1=2 hours) x 70 healthy subjects x 39€ = 5460€.
- Estimated neuropsychological time (V2=1 hour) x 70 healthy subjects x 39€ = 2730€.
- Travel to the private neuropsychologist's office: Healthy control = maximum 4 days of consultation in private practice/ if we estimate inclusions per office = 1200km x 0.35 = 420€.
- 20 euros per healthy subject per visit: 40€ x 70 healthy subjects: 2800€.
- Purchase 2 BETL licenses / 360€ = 720€

- Reimbursement of patient transport time: 20 \*90 = 1800€
- Methodology : 1500€.
- Design of the randomization module under CleanWeb: 1000€.
- Statistical analysis, production of reports: 4000€.
- Administrative costs of setting up (1 external centre): 150 euro

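### Centre is left out of the randomisation strata and would almost never enter the A versus B analysis, which costs some precision but does not bias the comparison

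*Protocol*

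**What the plan says.** The research characteristics in section 1.1 call the trial "Multicentric". Under 1.14 (patient course), patients are informed at their own centres, a psychologist presents the application to those allocated to it, and individual randomisation runs through an online module with "stratification by age (+/-5 years) and socio-educational level (+/- 2 years of study) and a randomization block of 4". Centre is not among the factors.

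The number of centres appears only for the healthy controls, who are "recruited through posters and on a voluntary basis in the 4 centers". The budget lists "Administrative costs of setting up (1 external centre): 150 euro", so the number of patient-recruiting centres is not certain. Centre is recorded for every subject, because section 1.15 builds the identifier partly from "a number for the number of the center".

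For the main analysis, section 1.19 says "the comparison of the mean number of connections will first be carried out by a parametric (Student's t) mean comparison test", or its rank-based equivalent. A linear regression follows only for parameters found to differ significantly between the two groups, with stepwise selection. Centre is not named.

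**The concern.** The primary endpoint, weekly connections, measures engagement. How the tool is introduced, and which patients a site recruits, could plausibly affect it. If so, centre is prognostic, and two choices in the protocol leave it uncontrolled.

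First, with centre outside the strata, the A:B split within a centre is left to chance. Second, the rule in 1.19 selects covariates by whether they happen to be imbalanced, not by whether they predict the outcome. A strongly prognostic centre effect would therefore usually stay out of the model, and if it did qualify, stepwise selection could still drop it.

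At stake are the precision of a comparison fixed at 30 versus 30 and the credibility of the one allocation that is actually realised.

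**Working it through.** **Inputs from the protocol.** 30 patients in each of A, B and C (1.8); individual allocation (1.14); t-test or Mann-Whitney without centre, 5% threshold (1.19).

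**Assumptions, since the protocol gives no figures.** Four patient centres; sizes as stated below; outcome SD set to 1; a share ρ of outcome variance due to centre, from 0 to 0.20; two-sided testing. The protocol states no SD, absolute mean or planned power, so its group size of 30 cannot be reproduced. For scale, the standardised difference detectable with 80% power is (1.96 + 0.84) × √(2/30) = 0.72.

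**1. Chance imbalance.** Ninety patients were allocated 30/30/30 ignoring centre (simulation).

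| Centre sizes | At least one centre with A:B of 2:1 or worse | Largest A–B gap in a centre's share ≥ 10 points | ≥ 20 points |
|---|---|---|---|
| 23/23/22/22 | 48% | 86% | 31% |
| 45/20/15/10 | 70% | 82% | 26% |

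**2. How often 1.19 would admit centre.** Under randomisation, a 5% test of centre by arm is significant about 5% of the time by construction. Simulation gives 0.048 to 0.055. The figure does not depend on ρ.

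**3. Variance of the A–B difference.** Take 60 patients with centre shares p of 28/60, 14/60, 10/60 and 8/60.

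- Unstratified and unadjusted: variance = (2/30) × [(1 − ρ) + hρ], where h = (60/59) × (1 − Σp²).
- Σp² = (784 + 196 + 100 + 64)/3600 = 0.318, so h = 1.017 × 0.682 = 0.694.
- Stratified by centre, centre in the model, exact balance within centre: variance = (2/30) × (1 − ρ).

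| ρ | Unstratified, unadjusted | Stratified, adjusted | Reduction |
|---|---|---|---|
| 0 | 0.0667 | 0.0667 | 0% |
| 0.05 | 0.0656 | 0.0633 | 3.5% |
| 0.10 | 0.0646 | 0.0600 | 7.2% |
| 0.20 | 0.0626 | 0.0533 | 14.8% |

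These reductions assume perfect balance within each centre, so they are upper limits for these sizes. Simulation gives about 2–3%, 6–8% and 15% for ρ of 0.05, 0.10 and 0.20. Four equal centres would give 3.9%, 7.8% and 16.0% by the same formula (h = 0.763).

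**4. Level, bias and power.** Simulated with sizes 28/14/10/8, 6,000 runs per setting, true standardised effect 0.72.

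| ρ | Type I error, plain t-test, unstratified | Power, plain t-test, unstratified | Power, stratified with centre in the model |
|---|---|---|---|
| 0 | 0.051 | 0.78 | 0.79 |
| 0.05 | 0.055 | 0.80 | 0.80 |
| 0.10 | 0.051 | 0.79 | 0.82 |
| 0.20 | 0.047 | 0.82 | 0.86 |

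The mean estimate stays within 0.01 of the true value throughout. Adding centre to the model without stratifying gives power 0.80 at ρ = 0.10 and 0.84 at ρ = 0.20. Stratifying without modelling centre makes the t-test conservative (type I error 0.032 at ρ = 0.20), so the two changes belong together.

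**The case against.** The strongest reply is that individual randomisation already covers centre imbalance: it is chance, and the test and interval allow for it. That stands. The t-test keeps its level, and the loss is at most about 4 points of power over the range examined. The 48% and 70% figures describe how often some centre looks lopsided; in a centre contributing 10 of 90 patients a 5:2 split is ordinary. They do not measure error in the estimate.

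A second reply is that covariates may be left to an analysis plan that is not shown. This stands in part. Such a plan could add a centre term, but it cannot add a stratum after allocation, and the protocol already commits to a significance-triggered rule.

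A third reply is that centre strata can be harmful here. Crossing four centres with, say, six age bands and three education bands gives 4 × 6 × 3 = 72 cells for 90 patients; even without education, 24 cells hold 90/24 = 3.75 patients each, less than one block of four. Allocation is also open, so small fixed blocks within a centre are easier to guess. Both points stand and shape the fix.

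Two stronger readings are tempting. A reader might infer that centre differences in testing distort the A/B result. They do not: section 1.16 takes connections from the application's own file, so test administration bears only on the secondary cognitive scores. A reader might also infer that centre-based supervision inflates the type I error, since scheduled calls exist only in arm A. If callers formed four clusters in that arm, ignoring this would give 0.057 to 0.127 for intra-cluster correlations of 0.02 to 0.20. But the protocol does not say that each centre supervises its own patients, and stratifying by centre would not remove that problem.

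**Conclusion.** The point holds as a modest loss of efficiency. Centre is absent from the strata that 1.14 fixes, and the adjustment rule in 1.19 would bring it in only about one time in twenty, regardless of its effect on connections. The cost is chance imbalance and lost precision: between nothing and about 15% of the variance of the A–B difference as the share of variance due to centre goes from 0 to 20%, or roughly 0 to 4 points of power.

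The documents do not support a claim of systematic bias or of an invalid primary test. The size rests on assumed centre numbers, centre sizes and variance shares. The protocol documents no centre effect, and its count of centres needs reconciling between 1.14 and the budget.

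**What to change.** In 1.14, make centre a stratification factor and keep the total number of strata small, for example centre with one coarse, explicitly banded factor, or use minimisation. Use block sizes that vary and are multiples of three. The present block of 4 does not divide evenly among A, B and C although "This individual randomization will be done according to a 1:1 ratio", and a fixed small block is predictable in an open trial. State how many centres recruit patients.

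In 1.19, pre-specify centre as a fixed term in the A versus B model, whether or not it differs between arms, with small centres pooled by a rule set in advance (for example, fewer than about 6 patients). If allocation has already begun, this half can still be adopted before the data are analysed and keeps part of the gain.

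Cost: a change of settings in the randomisation module and one model term, using a centre number already in the subject code. The model uses up to 3 of the t-test's 58 degrees of freedom (60 − 2 = 58 becomes 60 − 5 = 55). Balance on education is looser if that factor is dropped, and allocation becomes somewhat more predictable within a centre, which varied blocks limit.
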